After completion of informed consent and the Screening Visit, participants will be randomly assigned (1:1 ratio) to the Treatment or Waitlist Control groups, and will be notified of their condition in person or via secure e-mail or phone.

IV. Study Procedures

a. Study Visits

All Treatment Group participants will complete a packet of assessments at the Screening Visit, on the day of training (considered baseline assessment), and at 2-week, 1-month, 2-months, and 3-months following the baseline assessment. The Treatment Group will also participate in-person with a Follow-up Group Qualitative Interview.

All Control Group participants will complete a packet of survey assessments at the Screening Visit; the baseline assessments within five days of the Treatment Group's training; and at 2-week, 1-month, 2-months, and 3-months post baseline. On the day of the Control Group's training (to be scheduled approximately 3 months after screening), the Control Group participants will complete the assessments related to the training (P-CPI Knowledge Based Assessment and P-CPI Course Evaluation Assessment). Every effort will be made to have Control Group participants complete their baseline assessments in person but these assessments may be completed remotely for those participants unable to visit the Lurie Center in person within the five-day window.

The measures above will be presented using a counterbalanced design in order to reduce the chances that the order of the measures adversely impacts the results.

To help participants defray costs of travel and compensate them for their time, we will provide participants a total of \$150.00 for their participation in the form of a check. Compensation will be prorated with payment of \$25 for completion of each of the following: Screening Visit, Training Visit, 2-week assessments, 1-month assessments, 2-month assessments, and 3-month assessments.

b. Treatment and Control Groups

Parents will be permitted to pursue medical care, support and/or therapeutic services as they typically would during study participation, except for other parent behavior training services.

Treatment Group:

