The treatment group (n=30) will receive a one-day (6-hour) training in CPI's Nonviolent Crisis Intervention® including the use of nonverbal, paraverbal, verbal, and physical intervention techniques. The Lurie Center has worked with CPI to modify their current parent and caregiver curriculum to include appropriate physical intervention techniques into a revised workbook, CPI Training for Parents®, that will be given to each participant and followed during the training. There will be 3-4 trainings offered to achieve the sample size of 30 with 6-12 subjects per group.

Waitlist Control Group:

The Waitlist Control group (n=30) will receive the same one-day (6-hour) training in CPI's Nonviolent Crisis Intervention® including the use of nonverbal, paraverbal, verbal, and physical intervention techniques 3 months after the completion of the baseline assessments.

c. Parameters to be Measured

The following assessments will be administered in this investigation based on the schedule outlined in Section "D" below. All measures (with the exception of the P-CPI Knowledge Based Assessment and P-CPI Course Evaluation Assessment which are original measures unique to this study) have been selected based on construct validity and have been evaluated for sound psychometric properties by the investigators.

DSM-5 Checklist for Autism Spectrum Disorder: The proposed DSM-V criteria for ASD will be documented in the form of a checklist for an MD/PhD to complete.

Inclusion/Exclusion: A checklist will be completed to ensure all inclusion and exclusion criteria are met.

Demographics Review: Information such as age, race, ethnicity, family status, address, phone number, and e-mail address will be collected.

Aberrant Behavior Checklist (ABC; Aman, Singh, Stewart, and Field, 1985). The ABC consists of five subscales and takes about 10-15 minutes to complete. The ABC checks symptoms of irritability and agitation, lethargy and social withdrawal, stereotypic behavior, hyperactivity and non-compliance, and inappropriate speech.

Parenting Stress Index-Short Form (PSI-SF; Abidin, 1995). The PSI-SF is a self-report measure of severity and domain of parenting stress which includes 36 items rated on a 5-point, Likert scale. The PSI-SF has been the single most utilized measure of parenting stress, particularly in the ASD literature (e.g., Davis & Carter, 2008; Hall & Graff, 2011).

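### Waitlist training is timed from screening in Section IV.a but from baseline in IV.b, so controls may be trained before their 3-month assessment, which would weaken the exploratory Hypothesis VI contrast

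*Combined protocol and SAP*

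**What the plan says.** The plan gives two times for one event. Section IV.a (Study Visits) has the Control Group's training "to be scheduled approximately 3 months after screening". Section IV.b (Waitlist Control Group) has it "3 months after the completion of the baseline assessments".

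Control follow-up is counted from baseline. IV.a asks controls for "the baseline assessments within five days of the Treatment Group's training" and for further packets "at 2-week, 1-month, 2-months, and 3-months post baseline".

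Screening and baseline are separate occasions. Section III.c randomizes after the Screening Visit, the schedule in IV.d gives the two visits their own columns, and Section VI uses the screening score as a covariate with baseline as a level of time. No section limits the interval between them.

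IV.a treats control training as a group event ("On the day of the Control Group's training") and lists only the knowledge and course-evaluation forms for that day. The plan does not say whose date the session is timed from, or that the 3-month packet must come first.

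Hypothesis VI, which is exploratory, compares changes at 1, 2 and 3 months between the arms. Section VI brings in those measurements using all observed data. It has no rule for a control's score recorded after that control's own training.

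**The concern.** The comparison is between trained parents and parents who are still waiting. Controls "will receive the same one-day (6-hour) training" as the treatment arm, so a control who has attended is no longer an untrained comparator.

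If the 3-month control scores mix trained and untrained parents and the training works, the difference between arms shrinks. Three months is the plan's last between-arm look, so a benefit that lasted could be read as one that faded. Without recorded training dates and a handling rule, a reader could not tell the two apart.

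**Working it through.** **The plan's own figure.** Section V claims more than 80% power for a two-sample t-test with 27 per group and a standardized effect of 0.8. With two-sided alpha 0.05, the noncentral t gives 82.2%. Allowing for 10% dropout, 27 / 0.9 = 30 per group. The figure reproduces, and nothing below changes it.

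**Timing under IV.a.** Take 3 months as 91 days, 2 months as 61 and 1 month as 30. Let B be a control's baseline date and S the screening date from which the session is timed.

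- Training falls at S + 91 and the 3-month packet at B + 91.
- Training therefore leads the 3-month due date by L = (B + 91) − (S + 91) = B − S.
- Training comes before a packet due d days after baseline when L > 91 − d.

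| Packet | d | Training comes first if L exceeds |
|---|---|---|
| 3-month | 91 | 0 days |
| 2-month | 61 | 30 days |
| 1-month | 30 | 61 days |
| 2-week | 14 | 77 days (77 / 7 = 11 weeks) |

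The plan gives no value for L. As an assumed range, leads of 7, 14, 28 and 42 days put training at days 84, 77, 63 and 49 after baseline. All four precede day 91, and only the last precedes day 61.

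L depends on which screening date is used:

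- Timed from a control's own screening, L is that control's own gap.
- Timed from the first person screened, the largest L is the last control baseline minus that first screening date.
- Timed from the last person screened, L is smaller but not known to be zero, because the interval from that screening to the Treatment Group session is also unstated.

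**Timing under IV.b.** Training and the 3-month packet are both due at B + 91, so L is nominally 0 and the order is undefined.

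**Effect on the contrast.** Let D be the true 3-month effect, p the share of controls trained before the packet, and k the fraction of D that such a control has gained by then. Suppose that being trained first is unrelated to outcome. With c the mean change without training:

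- P-CPI mean change = c + D
- WLC mean change = c + pkD
- Difference = D(1 − pk)

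The documents give none of D, p or k. As pk runs from 0 to 1, the contrast runs from D to 0. If D = 0, there is no bias of this kind.

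**Primary and secondary comparisons.** The Section VI models for Hypotheses I–V use only the baseline and 2-week levels of time. A control's 2-week score is exposed only if L exceeds 77 days.

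**The case against.** The best defence is that IV.b is the operative rule. It defines the waitlist arm and is unqualified, whereas the IV.a wording is a parenthesis softened by an approximation, in a sentence about forms. IV.a also lists follow-up to 3 months before it mentions control training, and gives training day only two training forms. That fits packet first, then training. This is a fair reading and the conflict may be a drafting slip. But no section states the order, and IV.b by itself makes the two coincide.

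It is also fair that the harm is narrow. It needs IV.a to be followed (or training to come first under IV.b), a lead of some length, and a training effect, and it falls on exploratory comparisons in a pilot study. Short leads would do little. The CAPES-DD and FQOL are modified to ask about the previous two weeks, so a lead of a few days leaves much of that window before training.

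Some stronger readings do not hold:

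- A reader might infer that the primary result or the power is compromised. That would need a lead above 11 weeks, which nothing in the plan suggests.
- A reader might attach a figure to the loss of power at 3 months. Any such figure would rest on invented values of p, k and D.
- A reader might infer that IV.b alone produces a lead of 5 to 10 days, because control baselines can spread over the window. That needs baselines that fill the window and a session timed from the earliest of them.
- A reader might take the bar on outside services ("except for other parent behavior training services") as a rule that controls stay untrained until 3 months. It covers all parents and other services, and says nothing about when controls receive P-CPI.

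**Conclusion.** The point holds, as an inconsistency that should be fixed. IV.a and IV.b set different times for waitlist training. Following IV.a trains a control before the 3-month packet whenever that control's baseline is later than the screening date used, and before the 2-month packet if it is later by more than about 30 days. Following IV.b leaves the order open.

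If training works, controls trained first bias the 3-month contrast of Hypothesis VI toward no difference. The direction is clear under that condition, but the size cannot be computed. The 2-week comparisons and the stated power stand unless the lead exceeds about 11 weeks. The day counts assume months of 30, 61 and 91 days and take the approximate timing in IV.a at its nominal value.

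**What to change.** 1. In both IV.a and IV.b, state that waitlist training takes place after the 3-month post-baseline assessment.
2. Schedule each control session after the 3-month due date of the last control attending it. Have any control with an outstanding packet complete it before training starts that day. Do not hold the session for late or missing packets: Section II plans to enroll 100 to obtain 60 completers, so some packets will not come back, and one of them could delay the whole group.
3. Record each control's training date.
4. Add to Section VI that the 3-month comparison will be reported with and without any control scores recorded after that control's own training. Both are needed, because dropping such scores removes data from one arm only. The planned mixed model already accepts partly observed outcomes.

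The cost is wording in two sections, one recorded date and one sentence of analysis. Some controls wait slightly longer. If a session serves controls from a single Treatment Group session, baseline spread adds at most 10 days for the earliest control (5 + 5, if the five-day window runs either side), or 5 if it runs only after. Compared with IV.a, the session also moves back by whatever lead that section would have created. Sample size and power do not change.
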